8.3.2.1. Primary Outcomes (Birth outcomes)

- Major congenital malformations, any and specific, according to the European Network of Congenital Anomaly Registers (EUROCAT) classification²⁰
- Stillbirth, as recorded in each country's birth registry
- Low birth weight (birth weight < 2500 g)
- Small for gestational age (SGA), defined, for singleton pregnancies, as a dichotomous variable (yes/no) of birth weight below 2 standard deviations (SDs) of sex- and gestational week specific distributions, using country-specific reference standard.^{19,21} SGA non-singleton gestations will be defined if appropriate reference standard can be defined/identified; otherwise set to missing.
- Preterm birth, defined as gestational age <37 weeks
- Low Apgar score at 5 minutes, defined as a dichotomous variable (score 0-6 vs. score 7-10)
- Microcephaly, defined as a dichotomous variable (yes/no) of head circumference at birth (cm) smaller than 2 SD of sex- and gestational week specific distribution, using country-specific reference standard

8.3.2.2. Secondary Outcomes (Postnatal neurodevelopmental outcomes)

- Attention deficit hyperactivity disorder (ADHD) (identified via inpatient or outpatient hospital diagnosis or a medication proxy)
- Autism spectrum disorders (ASD) (identified via inpatient or outpatient hospital diagnosis)
- Learning disabilities (including mental retardation)(identified via inpatient or outpatient hospital diagnosis)

8.3.2.3. Sensitivity Analysis Outcomes (Major congenital malformations)

- Major congenital malformations identified at live or stillbirths or 2nd trimester abortions, any and specific as described above (Denmark, Finland, Norway)

8.3.2.4. Other Outcomes

- Major congenital malformations identified in the total study population of live or stillbirths, to provide context

8.3.3. Covariates and other population characteristic

Characteristics of the study population will include perinatal covariates and covariates of the mother. Perinatal covariates include calendar year of delivery, maternal age at conception, parity (number of live and still births prior to the on-study pregnancy); marital/cohabiting status; pregravid body mass index (BMI) as recorded at the first antenatal visit or via a hospital diagnosis of obesity; smoking during pregnancy as recorded at the first antenatal visit; single or multiple gestation; Caesarean delivery; and child's sex. Caesarean delivery and child's sex will be reported but will not be used for adjustment. Indication for pregabalin use in 12-months pre-LMP (epilepsy, neuropathic pain, GAD and related disorders) will be reported descriptively but will not be used for adjustment.

[figure not shown]
Covariates of the mother considered for adjustment (inclusion in propensity-score model) will include:

- calendar year of delivery;
- age in years at conception;
- marital/cohabiting status;
- smoking during pregnancy;
- Obesity (BMI ≥ 30 kg/m²) or a hospital diagnosis of obesity;
- Single or multiple gestation
- hospital-recorded morbidity based on inpatient and outpatient specialist care or proxy medication use in 12 months pre-LMP: migraine or other headache syndromes, other neurologic disorders, depression, bipolar disorder, alcohol abuse or dependence, drug abuse or dependence, hypertension, haematological diseases, diabetes, asthma, liver diseases, renal impairment, rheumatic diseases, obesity, disorders of female pelvic organs/genital tract, thyroid disorders, infections [infections will be assessed in 90 days pre-LMP]. In Finland, in addition to the hospital diagnoses, diagnoses from primary care are also available and will be used;
- indicators of maternal health care utilisation in the 12 months pre-LMP (number of inpatient and specialised outpatient encounters);
- for the outcome congenital malformations: maternal medication use each as a dichotomous variable, defined by at least one dispensing during the first trimester (AEDs, antidepressants, hypnotics, antipsychotics, analgesics, antihypertensives, non-steroidal anti-inflammatory drugs, drugs for peptic ulcer/gastroesophageal reflux, folic acid, drugs for in-vitro fertilization, thyroid hormones, systemic corticosteroids, and antiinfectives for systemic use);
- for the outcomes other than congenital malformations: maternal medication use each as a dichotomous variable, defined by at least one dispensing during any trimester (AEDs, antidepressants, hypnotics, antipsychotics, analgesics, antihypertensives, non-steroidal anti-inflammatory drugs, drugs for peptic ulcer/gastroesophageal reflux, folic acid, drugs for in-vitro fertilization, thyroid hormones, systemic corticosteroids, and antiinfectives for systemic use).

[figure not shown]
Full list of the study variables and their operational definitions are provided in [Annex 3](#).

Figure 2. Examples of follow up period for neurodevelopmental outcomes during the study period

[figure not shown]
1.

2.

3.

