6. RATIONALE AND BACKGROUND

Pregabalin (Lyrica[®], Pfizer Inc., New York, NY) was approved in July 2004 by the European Medicines Agency (EMA) for the treatment of peripheral neuropathic pain and as an adjunctive therapy for adult patients with partial onset seizures. Subsequently, the marketing authorizations were expanded to include generalized anxiety disorder (GAD), in March 2006 and central neuropathic pain, in September 2006. Per current European Union (EU) label, “Lyrica[®] should not be used during pregnancy unless clearly necessary (if the benefit to the mother clearly outweighs the potential risk to the foetus).”¹ In the general population (including men and women of all ages), pregabalin is mostly used for neuropathic pain (18-98%) and least used for epilepsy (4-6%).² Use of pregabalin in non-pregnant population, as assessed in a study in Sweden, is primarily for neuropathic pain (36%) and only 1.3% for epilepsy, with 40% of pregabalin initiators having no identifiable approved indication based on routine records.³ Published data on the most common indication in pregnant women are unavailable at this time. A study based on two distinct United States (US) datasets reported an epilepsy indication frequency of 5.5% and 6.7% of pregabalin use in pregnant women.⁴ In the feasibility assessment for this study, based on available Danish data, 21% of pregnancies exposed to pregabalin in the first trimester had a known indication identifiable by a hospital diagnosis in the previous year. Those included epilepsy (4% of those with identifiable indication), neuropathic pain (72% of those with identifiable indication), or GAD (24% of those with identifiable indication). Frequency distributions were similar for pregnancies exposed to pregabalin at any trimester (Table 1).

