(AED) in Europe, thus having an additional advantage of helping improve study precision.⁶ In Europe, lamotrigine, alone or in combination with other AEDs, is indicated for treatment of epilepsy, partial and generalised seizures, including tonic-clonic seizures and the seizures associated with Lennox-Gastaut Syndrome in adults.⁷ Lamotrigine is also indicated for treatment of bipolar disorder.⁷ Lamotrigine has not been associated with an increased risk of congenital malformations.⁸ In the feasibility assessment for this study, based on available Danish data, the following distribution of known pregabalin indications were identified for pregnancies exposed to lamotrigine in the first trimester: epilepsy (79% of those with identifiable indication), neuropathic pain (10% of those with identifiable indication), or GAD (10% of those with identifiable indication). Frequency distributions were similar for pregnancies exposed to lamotrigine at any trimester (Table 1). Duloxetine has been approved in the EU since 2004 for treatment of GAD, depressive disorder, major diabetic neuropathies and, since 2014, for treatment of neuralgia.⁹ Available data, albeit sparse, do not suggest clinically important risk increase associated with duloxetine use in pregnancy.¹⁰⁻¹² In the feasibility assessment for this study, conducted using Danish data, the following pregabalin indication frequency estimates were reported for pregnancies exposed to duloxetine in the first trimester: epilepsy 7% (among those with identifiable indication); neuropathic pain 48% (among those with identifiable indication); GAD 45% (among those with identifiable indication) (Table 1).

Table 1. Pregabalin indication frequency proportions

	Source of data (N with recorded diagnosis)	Epilepsy (%)	Neuropathic pain (%)	GAD (%)
General population (United Kingdom) ²	Pregabalin DUS (13,480)	4-6	18-98	7-28
Non-pregnancy population (Sweden) ³	Pregabalin DUS (18,626)	1	36	4
Pregabalin (Denmark [A0081359]) (Feasibility assessment of this study)	First trimester (74)	4	72	24
	Anytime during pregnancy (117)	3	56	40
Lamotrigine (Denmark, [A0081359]) (Feasibility assessment of this study)	First trimester (675)	79	10	10
	Anytime during pregnancy (1164)	77	9	14
Duloxetine (Denmark, [A0081359]) (Feasibility assessment of this study)	First trimester (87)	7	48	45
	Anytime during pregnancy (179)	4	35	61

DUS, drug utilization study; GAD, generalised anxiety disorder.

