8.7.3.1. Computation of propensity scores

To account for confounding by the measured covariates, adjusted analysis will be conducted using propensity score (PS) stratification, following the approach by Paterno et al.⁴ For each pregnancy, a PS will be computed, using logistic regression, as the probability being exposed to pregabalin vs. given comparator conditional on the measured covariates listed in [Section 8.3.3](#) and [Annex 3](#).⁵³

PS will be estimated for each pregnancy using a generic-outcome model, meaning that all prespecified covariates will be included in the PS-estimating model, regardless of the outcome. Wyss et al showed, in a simulation study, that such model performs well when multiple outcomes are being examined;⁵⁴ furthermore, it is reasonable to assume in this study that all confounders distort the association in the same direction for all outcomes. In case of model non-convergence, covariates with the smallest cell counts (corresponding to the lowest prevalence of covariates) will be removed one-by-one until convergence is achieved.

A separate PS will be estimated for each study population and contrast. To summarise, the following sets of propensity scores will be estimated:

1. First-trimester pregabalin vs. first-trimester unexposed
2. First-trimester pregabalin vs. first-trimester lamotrigine
3. First-trimester pregabalin vs. first-trimester duloxetine
4. First-trimester pregabalin vs. first-trimester duloxetine or lamotrigine
5. First trimester pregabalin monotherapy vs. first-trimester unexposed
6. First trimester pregabalin monotherapy vs. first-trimester lamotrigine monotherapy
7. First trimester pregabalin monotherapy vs. first-trimester duloxetine monotherapy
8. First-trimester pregabalin monotherapy vs. first-trimester duloxetine or lamotrigine monotherapy
9. Any-trimester pregabalin vs. any-trimester unexposed
10. Any-trimester pregabalin vs. any-trimester lamotrigine
11. Any-trimester pregabalin vs. any-trimester duloxetine
12. Any-trimester pregabalin vs. any-trimester duloxetine or lamotrigine
13. Any-trimester pregabalin monotherapy vs. unexposed
14. Any-trimester pregabalin monotherapy vs. any-trimester lamotrigine monotherapy
15. Any-trimester pregabalin monotherapy vs. any-trimester duloxetine monotherapy
16. Any-trimester pregabalin monotherapy vs. any-trimester duloxetine or lamotrigine monotherapy

After estimation of each PS, the following steps will be taken in each country:

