8.9. Limitations of the research methods

All epidemiologic studies are subject to biases that may include confounding, information bias, and selection bias. As with most pharmacoepidemiologic studies, confounding by indication may be introduced since epilepsy itself is known to be associated with adverse pregnancy outcomes. Other sources of confounding include residual confounding by unmeasured characteristics and resulting from misclassification of confounders. Even though this study proposed to use not only unexposed pregnancies but pregnancies exposed to medications with indications similar to pregabalin, those latter comparisons may still be confounded. As suggested by the feasibility analyses (pilot data), the distribution of the indications for the comparator drugs may not be identical to that of pregabalin and this could also result in confounding. Furthermore, validity of diagnostic codes used to identify GAD have not been studied in any of the registers; in fact, most patients who actually do have such a disorder do not get that specific diagnosis, and may be assigned a less specific anxiety diagnosis instead. Assessing safety of pregabalin within each indication of use does not appear feasible as data on indication are available for a minority of pregnancies according to the pilot data.

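### Recorded indication is barred from the propensity score although pilot data show 4% v 79% epilepsy against lamotrigine; parity and the 21% figure also need reconciling

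*Protocol*

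**What the plan says.** **Indication.** Section 8.3.3 names epilepsy, neuropathic pain and, in its own words, "GAD and related disorders) will be reported descriptively but will not be used for adjustment". Section 6 presents lamotrigine and duloxetine as the means of controlling confounding by indication, because the registries do not identify all pregnancies with a relevant indication. In the same section, the Danish pilot figure for lamotrigine in the first trimester is "epilepsy (79% of those with identifiable indication"; Table 1 gives 4% for pregabalin and 7% for duloxetine. Section 8.9 states that "epilepsy itself is known to be associated with adverse pregnancy outcomes".

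**Recording.** Section 6 reports that "21% of pregnancies exposed to pregabalin in the first trimester had a known indication" identifiable from a hospital diagnosis in the previous year.

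**Parity.** Section 8.3.3 lists "parity (number of live and still births prior to the on-study pregnancy" among the perinatal covariates. It then says "Caesarean delivery and child's sex will be reported but will not be used for adjustment", and makes the same statement for indication. The bullets under "Covariates of the mother considered for adjustment (inclusion in propensity-score model) will include" do not name parity. Section 8.7.3.1 conditions the propensity score on the covariates listed in Section 8.3.3 and Annex 3, and has all prespecified covariates enter the model.

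**The concern.** Two of the four contrasts carry a risk factor that the protocol names, extracts and shows to be badly imbalanced, but does not allow the propensity score to use. If epilepsy raises the outcome risk, its concentration in the lamotrigine group raises the comparator's risk and pulls the pregabalin ratio down. In a safety study that is the direction that can hide harm.

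The planned checks may not show this. The balance rule in Section 8.7.3.1 is set out for covariates, and a variable barred from adjustment need not be tested against it. Section 8.1 infers confounding from differences between comparators, but those differences may partly reflect the epilepsy mix. The listed covariates are uncertain substitutes. An indicator for AEDs is constant in the lamotrigine contrast if it counts the study drugs, and constant in the monotherapy contrasts if it means other AEDs. Whether other neurologic disorders covers epilepsy depends on Annex 3 codes that are not shown.

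**Working it through.** **Inputs.**
- Table 1, Denmark, first trimester, number with a recorded indication and epilepsy share: pregabalin 74, 4%; lamotrigine 675, 79%; duloxetine 87, 7%.
- Table 4, Denmark, first trimester, all exposed: 200, 2,000 and 400.
- Section 8.7.3.1: a standardised mean difference (SMD) below 0.1 counts as balanced.
- Risk ratio R for epilepsy and outcome: not in the protocol. I assume 1.1, 1.5 and 2.0.

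**1. The plan's 21%.** 74/0.21 = 352. Against Table 4, 74/200 = 37%, while 74/350 (the any-time pregabalin count) = 21%. The any-time figure is 117/350 = 33%. The stated 21% fits the any-time denominator, not the first-trimester one.

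**2. Epilepsy share in the combined comparator** (ignoring women dispensed both drugs). Denmark, recorded: (0.79×675 + 0.07×87)/762 = 539/762 = 71%. Weighted by the four-country counts in Table 4 (6,200 lamotrigine, 1,800 duloxetine): (0.79×6,200 + 0.07×1,800)/8,000 = 63%. With the Finnish counts (900 and 500): 746/1,400 = 53%.

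**3. Lower-bound prevalences.** If every pregnancy without a recorded indication is epilepsy-free: pregabalin 0.04×74/200 = 1.5%; lamotrigine 0.79×675/2,000 = 26.7%; combined 539/2,400 = 22.5%; duloxetine 0.07×87/400 = 1.5%.

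**4. Imbalance.** SMD = (p1 − p0)/√{[p1(1−p1) + p0(1−p0)]/2}. With the recorded mix: lamotrigine −2.35, combined −1.91, duloxetine −0.13. At the lower bound: lamotrigine −0.78, combined −0.68.

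**5. Bias factor without adjustment** = [1 + p1(R−1)]/[1 + p0(R−1)]. Example, lamotrigine, recorded mix, R = 1.5: 1.02/1.395 = 0.73.

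| Contrast | Prevalences | R = 1.1 | R = 1.5 | R = 2.0 |
|---|---|---|---|---|
| Lamotrigine | lower bound | 0.98 | 0.89 | 0.80 |
| Lamotrigine | recorded mix for all | 0.93 | 0.73 | 0.58 |
| Combined (Danish mix) | lower bound | 0.98 | 0.91 | 0.83 |
| Combined (Danish mix) | recorded mix for all | 0.94 | 0.75 | 0.61 |
| Duloxetine | recorded mix for all | 1.00 | 0.99 | 0.97 |

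**6. What adjustment would recover.** Suppose a share s of true epilepsy is recorded in both arms and comparators are weighted to the exposed. The unrecorded stratum of the comparator then has epilepsy prevalence q0 = p0(1−s)/(1−p0·s), and with w = p1·s the residual factor is [1 + p1(R−1)]/{wR + (1−w)[1 + q0(R−1)]}. For lamotrigine at 4% v 79% and R = 1.5: 0.73 with no adjustment, 0.77 at s = 0.5, 0.83 at s = 0.8, and 1.00 at s = 1.

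If the recorded mix applies to everyone, s is fixed by the Danish counts: 533 of 0.79×2,000 = 1,580, or 34%. Epilepsy alone then moves 0.73 only to 0.75. Adding all three recorded indications, treated as mutually exclusive, gives a weighted comparator prevalence of (3 + 126×0.79)/200 = 0.51 and a factor of 1.02/1.256 = 0.81. At the lower bound, where all epilepsy is recorded, adjustment takes 0.89 to 1.00.

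**7. Overlap.** 2,000 − 533 = about 1,470 Danish lamotrigine pregnancies have no recorded epilepsy, so comparators remain for the pregabalin group.

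**8. Parity.** Nothing to compute. Section 8.3.3 lists it as a covariate and does not exclude it, Section 8.7.3.1 can be read to include it, and the propensity-score bullets leave it out.

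**The case against.** The case for leaving the plan alone is substantial. The protocol discloses the problem: Sections 8.1 and 8.9 say that active-comparator contrasts may still be confounded and that indication mixes may differ. It gives low sensitivity of the indication data as a reason for using active comparators. Exposed versus unexposed is the primary comparison in Section 6, and the duloxetine contrast already has little epilepsy imbalance. Section 6 also says lamotrigine has not been associated with malformations, which points to a low epilepsy risk ratio for that outcome. The Danish mix need not hold elsewhere. The fix also removes least where the assumed bias is largest.

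Most of this limits the size rather than the point. Low sensitivity explains why analysis within indication is not feasible. It does not explain excluding an extracted variable when depression and bipolar disorder, taken from the same kind of records, are adjusted for.

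Four stronger readings are tempting but unsupported:
- That preterm and growth outcomes are confounded by parity. The protocol gives no parity distribution by exposure and no parity–outcome association, and does not bar parity.
- That the protocol calls epilepsy a cause of adverse outcomes. It says only that they are associated.
- That 0.73 is the expected bias. It rests on an assumed risk ratio of 1.5 and on the Danish recorded mix holding for every pregnancy, and it describes the contrast before any propensity-score adjustment.
- That correcting 21% to 37% defeats the low-sensitivity argument. Section 6 makes that argument without resting it on the figure, and 37% is still a minority.

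**Conclusion.** The point stands, with moderate weight. The bar on indication is explicit, and on the protocol's own pilot data the epilepsy imbalance in the lamotrigine and combined contrasts far exceeds the 0.1 balance limit, even if unrecorded means no epilepsy. Those contrasts are open to downward confounding: for lamotrigine, a factor of 0.98 to 0.80 at the lower-bound prevalences and 0.93 to 0.58 with the recorded mix throughout, for assumed risk ratios of 1.1 to 2.0. The duloxetine contrast is not materially affected (0.97 to 1.00).

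The direction holds for epilepsy only. Recorded neuropathic pain (72% v 10%) and GAD (24% v 10%) are more common with pregabalin than with lamotrigine, and the protocol gives no outcome association for either, so the net effect of all three indications is unknown.

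Parity is an internal inconsistency in wording, with no demonstrated bias. The 21% does not agree with Tables 1 and 4. Table 4 is rounded and estimated, and the period of the pilot data is not stated, so a swapped denominator is a likely explanation but not an established one.

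**What to change.** - **Indication.** Add recorded epilepsy, neuropathic pain and anxiety/GAD (12 months before LMP) to the propensity score for the lamotrigine, duloxetine and combined contrasts, or at least prespecify a parallel adjusted analysis that does so. Report the SMDs of all three before and after weighting, whether or not they are in the model.
- **Interpretation.** State that this reduces confounding by indication without removing it, because recording is incomplete.
- **Non-convergence.** Section 8.7.3.1 drops the covariates with the smallest cells first. Only about 3 Danish pregabalin pregnancies (4% of 74) have recorded epilepsy, so say how the rule applies to that term and report any removal.
- **Parity.** Add one bullet to the propensity-score list in Section 8.3.3, so that four country analysts fit the same model.
- **The 21%.** Correct the figure or state its denominator and period.

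The variables are already planned for extraction, and a separate propensity score is already fitted for each contrast. The cost is some effective comparator size in the lamotrigine and combined contrasts, plus residual misclassification from unrecorded epilepsy and imperfectly coded pain and anxiety.

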8.4. Data sources

Data sources used to construct the analysis data set for this study are presented in Table 3. Within each country, records from all registries are linkable at the individual level by a unique national person identifier. For births recorded in the birth registries, a maternal unique identifier is a variable on the record of the offspring, enabling exact linkage between a given offspring and maternal history of medication dispensing or diagnoses before or during pregnancy.

Diagnosis in all countries are registered based on the ICD-10 coding system and accessed through registers as specified in Table 3. Similarly medications are classified according to the ATC coding system and accessed through prescription registers. The medical birth registers in the included countries furthermore contain similar information other relevant covariates (calendar year of delivery, maternal age at conception, parity; marital/cohabiting status; pregravid body mass index (BMI); smoking during pregnancy; single or multiple pregnancy; and child's sex.)

Validity of routine data in Nordic national registries has been found to be high in all countries.²²⁻³⁷ In Denmark, positive predictive value of diagnoses of cardiac malformations is 89%.³⁸ For drugs used chronically, there is also high level of agreement between general practitioner and dispensing records.³⁹ An agreement between dispensing records and drug use reported in the standard medical antenatal records included in the birth register was 69% for antiepileptics in Sweden.⁴⁰

Table 3. National registries in Denmark, Finland, Norway and Sweden and type of data available from each registry

Study variable/role	Type of data	Data source(s)	Coding system(s) used
Person identification (mothers and children)	Unique personal identifier for data linkage	Danish Civil Registration System ⁴¹ Danish Civil Registration System Finnish Medical Birth Register* National Registry of Norway Swedish Total Population Register ⁴²	N/A
Study population	Pregnancies ending in singleton/multiple live birth or stillbirth	Danish Medical Birth Registry Finnish Medical Birth Register* Medical Birth Registry of Norway Swedish Medical Birth Register Danish National Patient Registry ^{43,44}	A specific variable in each birth registry

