	Pregnancies ending in therapeutic 2nd trimester induced abortion	Finnish Register on Induced Abortions* Norwegian Register of Pregnancy Terminations (part of the Medical Birth Registry of Norway) Not available in Sweden	ICD-10

Table 3. National registries in Denmark, Finland, Norway and Sweden and type of data available from each registry

Study variable/role	Type of data	Data source(s)	Coding system(s) used
Exposure (for full list see Section 8.3.1)	Maternal dispensings of pregabalin, lamotrigine, duloxetine	Danish National Health Services Prescription Database ^{45,46} Finnish Prescription Register ⁴⁵ Norwegian Prescription Database ⁴⁵ Swedish Prescribed Drug Register ⁴⁵	ATC
		Outcome (for full list see Section 8.3.2)	Major congenital malformations
Birth weight, gestational age, Apgar score at 5 minutes, head circumference, stillbirth	Danish Medical Birth Registry Finnish Medical Birth Register* Medical Birth Registry of Norway Swedish Medical Birth Register	A specific variable in each birth registry	
Neurodevelopmental outcomes	Danish National Patient Registry ⁴³ Danish Psychiatric Central Research Register ⁴⁷ Danish Psychiatric Central Register Finnish Care Register for Health Care Finnish Register of Primary Health Care visits Norwegian Patient Registry ^{48±} Swedish National Patient Register ^{29,49} Danish National Health Services Prescription Database ^{45,46} Finnish Prescription Register ⁴⁵ Norwegian Prescription Database ⁴⁵ Swedish Prescribed Drug Register ⁴⁵	ICD-10 for diagnoses, ATC codes for drug proxies	
Characteristic of study population and covariates (for full list see Section 8.3.3)	Mother: age, parity, marital/cohabiting status, mode of delivery, smoking during pregnancy, BMI	Danish Medical Birth Registry Finnish Medical Birth Register* National Registry of Norway ⁵⁰ Swedish Medical Birth Register ⁴²	A specific variable in each birth registry
	Offspring: sex, multiplicity of gestation		

Table 3. National registries in Denmark, Finland, Norway and Sweden and type of data available from each registry

Study variable/role	Type of data	Data source(s)	Coding system(s) used
Maternal morbidity (including indication for pregabalin) Markers of health care utilisation		Danish National Patient Registry, ⁴³ Finnish Care Register for Health Care Finnish Register of Primary Health Care visits Norwegian Patient Registry ⁴⁸ Swedish National Patient Register ^{29,49}	ICD-10 for diagnoses, ATC for medication proxies

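### The propensity-score list in Section 8.3.3 omits parity without a stated reason while Section 8.7.3.1 can be read as including it; the two sections need to agree, with parity in

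*Protocol*

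**What the plan says.** Section 8.3.3 opens with the perinatal covariates. These include "parity (number of live and still births prior to the on-study pregnancy" and "pregravid body mass index (BMI) as recorded at the first antenatal visit". Two sentences then take variables out of adjustment. One states that "Caesarean delivery and child's sex will be reported but will not be used for adjustment"; the other does the same for the indication for pregabalin.

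The list for the score follows under the words "Covariates of the mother considered for adjustment (inclusion in propensity-score model) will include". It contains calendar year, age, marital status, smoking, obesity, single or multiple gestation, morbidity, health care use and medications. Parity is not there. BMI appears only as "Obesity (BMI ≥ 30 kg/m²) or a hospital diagnosis of obesity", and obesity is repeated among the morbidities.

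Section 8.4 describes the birth registers as holding "maternal age at conception, parity; marital/cohabiting status; pregravid body mass index (BMI); smoking during pregnancy", and Table 3 repeats both variables: "Mother: age, parity, marital/cohabiting status, mode of delivery, smoking during pregnancy, BMI".

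Section 8.7.3.1 conditions the score on the measured covariates of Section 8.3.3 and Annex 3. It says that every prespecified covariate enters the model whatever the outcome. It also has the score estimated by an analyst in each country.

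**The concern.** Parity precedes the outcomes and is related to fetal growth, preterm birth and stillbirth. The any-trimester scores serve those outcomes. The SGA definition in Section 8.3.2.1 uses sex- and week-specific reference standards, so it does not absorb parity. If the list is followed as written and parity still differs by exposure after adjustment, the adjusted prevalence ratios carry a bias that register data already held could remove. A bias shared by the countries would also survive inverse-variance pooling.

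The second problem is the conflict itself. One analyst may work from the list and another from the cross-reference in Section 8.7.3.1. The country estimates would then be adjusted for different things because the text is ambiguous, and not because balance required it.

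**Working it through.** **1. Where each perinatal covariate goes (Section 8.3.3)**

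| Covariate | In the score list | Barred from adjustment |
|---|---|---|
| Calendar year | yes | no |
| Maternal age | yes | no |
| Parity | **no** | **no** |
| Marital/cohabiting status | yes | no |
| BMI | as obese yes/no | no |
| Smoking | yes | no |
| Single/multiple gestation | yes | no |
| Caesarean delivery | no | yes |
| Child's sex | no | yes |

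Parity is the only one of the nine that is neither listed nor barred.

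**2. The cross-reference in Section 8.7.3.1.** Taken literally, all covariates named in Section 8.3.3 would enter. That would include Caesarean delivery and child's sex, which Section 8.3.3 rules out. Read subject to those exclusions, it brings parity in. Read as pointing to the score list alone, it leaves parity out. The visible text does not settle which is meant.

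**3. Precision.** No figure in the protocol concerns parity. The study-size figure in Section 8.5 serves to check the standard-error formula (3% prevalence, 1000 exposed, 119:1):

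exp[(1.960 + 0.842) × √(0.97/30 × (1 + 1/119))] = 1.6584, against the stated 1.65845.

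Table 4 gives 350 + 900 + 350 + 800 = 2,400 pregnancies exposed at any time. The exposed-group part of the SE of the log prevalence ratio is √((1 − p)/(2,400p)):

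- p = 10% (Table 5, preterm birth/SGA): √(0.9/240) = 0.061
- p = 2.3% (assumed for SGA if birth weight is roughly normal, since the definition is below 2 SD): √(0.977/55.2) = 0.133
- p = 0.6% (Table 5, stillbirth): √(0.994/14.4) = 0.263

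**4. Bias from omitting parity.** The protocol gives no distributions, so every input here is an assumption: first births in p1 = 30–35% of exposed and p0 = 43–45% of unexposed pregnancies, with a prevalence ratio (PR) of 1.5–1.8 for first against later births.

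Bias factor = [1 + p1(PR − 1)] / [1 + p0(PR − 1)]

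- Smallest: 35% vs 43%, PR 1.5: 1.175/1.215 = 0.967, log −0.033
- Largest: 30% vs 45%, PR 1.8: 1.240/1.360 = 0.912, log −0.092

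In standard errors this is 0.5–1.5 for a 10% outcome, 0.3–0.7 at 2.3% and 0.1–0.4 at 0.6%.

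The direction is not known. With 43% first births in the unexposed, a difference of 5–10 percentage points either way and a ratio of 1.3–2.0, the factor is 0.93–0.99 or 1.01–1.07.

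**5. Bias from BMI as obese yes/no (also assumed inputs).** For SGA, underweight 6% vs 4% at ratio 1.5 gives 1.030/1.020 = 1.010, and 8% vs 4% at ratio 1.8 gives 1.064/1.032 = 1.031.

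A five-category check balances the obese share and leaves the rest:

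- Categories: underweight, normal, overweight, and two obese classes.
- Unexposed 4/60/23/9/4%; exposed 8/48/22/12/10%.
- SGA ratios 1.7/1/0.85/0.85/0.9.
- Exposed mean 0.995. Unexposed mean, reweighted to 22% obese, 0.9646. Factor 0.995/0.9646 = 1.032.

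Over three assumed exposed distributions the factor is 1.01–1.02 for preterm birth, 1.01–1.03 for stillbirth and 1.01–1.03 for SGA.

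**The case against.** The strongest reply is that parity is already in. Section 8.7.3.1 covers the covariates of Section 8.3.3, parity is one of them, and the exclusions do not name it. On this view the list merely has a drafting gap. Annex 3, which is said to hold the operational definitions, is shown only as headings. This stands far enough that a reader should not infer that parity is settled as excluded. It does not remove the conflict.

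The size is also open to challenge. The factors above are marginal. Bias remains only where parity differs by exposure after adjustment for age, marital status, smoking, obesity, multiple gestation, morbidity, health care use and medications. Only the contrast with unexposed pregnancies is illustrated. In the assumed scenario the parity and underweight biases for SGA run in opposite directions. All of this stands.

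A reader might further infer that the balance check would miss the problem. The documents do not support that: Section 8.7.3.1 does not limit the standardised mean differences to modelled terms, and Section 8.7.4.1 tabulates population characteristics by exposure.

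On BMI, a hospital diagnosis of obesity can only feed a yes/no variable, so the binary term does use both sources. Finer BMI needs a rule for missing values. The BMI part is therefore optional.

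**Conclusion.** The point holds as a low-cost improvement. Section 8.3.3 omits parity from the score list without a reason, Section 8.7.3.1 can be read the other way, and the two must be reconciled. If the list is followed, the avoidable bias for preterm birth, SGA, low birth weight and stillbirth is about 0.91–0.97 under the stated assumptions. That is an outer range before the other covariates absorb any of it. For rare outcomes it is small against the standard error. Coarse BMI adds about 1–3%.

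Two stronger conclusions are not supported. One is that the omission would mask harm: that needs fewer first births among the exposed, which the protocol does not show. The other is that all six non-malformation birth outcomes are affected: nothing here establishes an effect on low Apgar score or microcephaly.

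**What to change.** - Add parity (0, 1, 2 or more) to the score list in Section 8.3.3.
- Have Section 8.7.3.1 refer to that list specifically, and align Annex 3 with it.
- Show parity in the balance tables for every contrast.
- Optionally, enter BMI as underweight, normal, overweight, obese and missing, keep the hospital obesity diagnosis as a separate term, and show BMI in the balance tables.

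No new data are needed, since the birth registers are stated to hold both variables. The cost is a few more parameters in each score model. The non-convergence rule in Section 8.7.3.1 removes the lowest-prevalence covariates first. Parity is therefore unlikely to be lost, but a rare underweight category could be dropped in the smallest countries. Where that happens, the report should say so.
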